10 SAFETY ANALYSES

All analysis of safety variables will be performed using the SS, MS, and AMS.

The AMS will be used for summaries of safety that include data from the Initial Treatment Period and Maintenance Treatment Period.

Summaries of safety will be presented for the Initial Treatment Period, Maintenance Treatment Period, and combined Initial and Maintenance Treatment Period unless specified otherwise.

10.1 Extent of exposure

Summaries for exposure will be provided. This consists of a descriptive summary of study medication duration in days. In addition, total study medication duration and time at risk will be summarized in years by treatment group and treatment period (ie, the Initial Treatment Period, the Maintenance Treatment Period, and the Initial and Maintenance Treatment Period). Summary of exposure in Maintenance Treatment Period will be on MS. The cumulative study medication duration will be summarized for study participants exposed for given durations of time. For the cumulative duration through Week 48 the following categories for duration will be used:

- >0 weeks
- ≥4 weeks
- ≥8 weeks
- ≥12 weeks
- ≥16 weeks
- ≥20 weeks
- ≥24 weeks
- ≥28 weeks
- ≥32 weeks
- ≥40 weeks
- ≥48 weeks

Definitions for study medication duration and time at risk in days are provided below for each period. Time at risk will be summarized in years. Time at risk in years is calculated by dividing the time at risk in days by 365.25.

Throughout this section, date of last clinical contact for each participant is defined as the maximum of (last visit date including SFU visit, last imputed AE start date, date of study termination or completion, last date of study drug administration).

10.1.1 Exposure during the Initial Treatment Period

Definitions for study medication duration (days) and time at risk (days) during the Initial Treatment Period are provided as follows:

10.1.1.1 Study medication duration (days)

Definitions for study medication duration (days) are provided as follows:

- Date of last dose in the Initial Treatment Period – Date of first dose in the Initial Period + [REDACTED]

Note: The use of [REDACTED] assumes a [REDACTED] dosing interval (bimekizumab [REDACTED] and placebo). For participants randomized to bimekizumab [REDACTED], this will be adjusted based on the dosing interval (eg, use Date of last bimekizumab dose in the Initial Treatment Period – Date of first dose in the Initial Period + [REDACTED]).

Note: If date of last dose in the Initial Treatment Period + [REDACTED] (or + [REDACTED] in the case of [REDACTED] dosing) extends to a date beyond the date of first dose in the Maintenance Treatment Period, then this calculation reverts to:

- Date of first dose in the Maintenance Treatment Period – Date of first dose in the Initial Treatment Period + 1.
- For participants who die during the Initial Period, if date of last dose in the Initial Period + [REDACTED] (or date of last bimekizumab dose in the Initial Treatment Period + [REDACTED] in the case of [REDACTED] dosing) extends to a date beyond the date of death, then this calculation reverts to:
 - Date of death – Date of first dose in the Initial Period + 1.

10.1.1.2 Time at risk (days)

Definitions for time at risk (days) are provided as follows:

- For participants who complete the Week 16 visit and continue to the Maintenance Treatment Period:
 - Date of first dose in the Maintenance Treatment Period – Date of first dose in the Initial Period + 1.
- For participants who discontinue on or prior to the final visit of the Initial Period, use the minimum of the following:
 - Date of last dose in the Initial Treatment Period – Date of first dose in the Initial Treatment Period + 141
 - The total number of days in the Initial Treatment Period (112 days). For AEs that emerged after 112 days but still within the 140 days window, those AEs would be

classified as TEAE, but will be excluded from the output based on the Initial Treatment Period. However, these AEs will be included in the AE summaries for Maintenance Treatment Period.

- Date of last clinical contact – Date of first dose in the Initial Treatment Period + 1.
- For participants who die prior to the final visit of the Initial Treatment Period: Date of death – date of first dose in the Initial Period +1.

10.1.2 Exposure during the Maintenance Treatment Period

Definitions for study medication duration (days) and time at risk (days) during the Maintenance Treatment Period are provided as follows:

10.1.2.1 Study medication duration (days)

Definitions for study medication duration (days) are provided as follows:

- Date of last dose in the Maintenance Treatment Period – date of first dose in the Maintenance Treatment Period + [REDACTED]

The use of [REDACTED] assumes a [REDACTED] dosing interval. For participants randomized to bimekizumab [REDACTED] in the Maintenance Treatment Period, this will be adjusted based on the dosing interval (eg, use Date of last bimekizumab dose in the Maintenance Treatment Period – date of first dose in the Maintenance Treatment Period + [REDACTED]).

Note: If date of last dose in the Maintenance Treatment Period + [REDACTED] (or [REDACTED] in the case of [REDACTED] dosing) extends to a date beyond the final visit date of the Maintenance Treatment Period (not including SFU), then this calculation reverts to:

- Final visit date of the Maintenance Treatment Period (not including SFU) – date of first dose in the Maintenance Treatment Period + 1.
- For participants who die during the Maintenance Treatment Period, then this calculation reverts to:
 - Date of death – Date of first dose in the Maintenance Treatment Period + 1.

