- **Treatment policy strategy:** All available data observed at the time point of interest will be considered, regardless of the occurrence of intercurrent events. This means the analysis includes on- and off-treatment values collected after study participants prematurely discontinued study treatment but agreed to remain on the study and continued to attend visits and provide assessments at those visits as well as values from study participants who received rescue antibiotic medication. Those observed values will be analyzed according to the study participant’s randomized treatment. Study participants for whom efficacy data cannot be obtained at the week of interest, despite attempts to retain them in the study, will have their data imputed using MI – MCMC / monotone.

The following table depicts which missing data handling approaches will be used based on endpoint priority (primary, secondary, other) and endpoint type (responder, continuous, ordinal).

Table 4–1: Missing data handling approach by endpoint priority and type

End-point Priority	Endpoint Type	Composite Estimand (NRI)	Modified Composite Estimand (MI)	MI (MCMC/Reference-based)	Tipping Point	Treatment Policy	Hypothetical Estimand	OC
Primary	Responder	S ^a	P	S ^a	S	S ^a		S
Secondary included in the statistical testing procedure	Responder	S ^a	P					S
	Continuous						P	S
Secondary not included in statistical testing procedure	Binary	X	X					X
	Continuous						X	X
Other	Responder	X ^d	X					X ^d
	Continuous						X	X ^b
	Ordinal						X ^c	X ^c

MI=multiple imputation, NRI=Nonresponder imputation, OC=Observed case, P=Primary method, S=Sensitivity method, X=Method to be used (no priority designated).

Note: Composite estimand (NRI) refers to the approach in which data preceded by the intercurrent event of study treatment discontinuation due to AE or lack of efficacy or receipt of rescue antibiotic medication are imputed as nonresponse, and other missing data are also imputed as nonresponse.

Note: Modified Composite Estimand (MI) refers to the approach in which data preceded by the intercurrent event of study treatment discontinuation due to AE or lack of efficacy or receipt of rescue antibiotic medication are imputed as nonresponse, and other missing data are imputed via a multiple imputation model.

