10.1.2.2 Time at risk (days)

Definitions for time at risk (days) are provided as follows:

- For participants who complete the Maintenance Treatment Period as planned and continue into an extension study (and, therefore, do not have the SFU visit in the feeder study):
 - Date of last visit of the Maintenance Treatment Period – Date of first dose in the Maintenance Treatment Period + 1.
- For participants who die prior to the final visit of the Maintenance Treatment Period:
 - Date of death – Date of first dose in the Maintenance Period + 1.
- For all other participants, use the minimum of the following:
 - Date of last dose in the Maintenance Treatment Period – Date of first dose in the Maintenance Treatment Period + 141 days.

- Date of last clinical contact – Date of first dose in the Maintenance Treatment Period + 1.

Note: This group could include participants who discontinue the Maintenance Treatment Period early, participants who complete the Maintenance Treatment Period as scheduled but choose not to continue into an extension study, or participants who are ongoing in the SFU period at the time of the data snapshot.

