10.2.1 Data considerations

Treatment-emergent AEs are defined as those AEs that have a start date on or following the first dose of study treatment through the final dose of study treatment + 140 days (covering the 20-week SFU period). If it is not possible (due to partial dates) to determine whether or not an AE is treatment-emergent then it will be assumed to be a TEAE.

An AE will be assigned to the Initial Treatment Period if it started between the first administration of IMP on Day 1 up to Week 16. An AE will be assigned to the Maintenance Treatment Period if it started between the Week 16 study drug administration and Week 48.

If an AE occurs on the date of a treatment switch, the event is attributed to the original treatment. The only exception to this is if the AE fulfills any of the criteria specified below:

- Events that fulfill the anaphylaxis criteria for acute events (refer to Appendix A in Section 12.1)
- Hypersensitivity events identified by the SMQ “Hypersensitivity (SMQ)” (see Section 12.1 Appendix A)
- Events with an high level term (HLT) of “Administration site reactions NEC”
- Events with an HLT of “Injection site reactions”

The rules for imputing partial start or stop dates are outlined in Section 4.2.4.

Any TEAEs that occur during the SFU Period will be attributed to the period in which the participant was before initiating the SFU Period.

Duration of AEs will not be calculated if there is missing stop date information.

If the intensity of an AE is unknown, it is considered as severe. If the relationship to study drug is missing, it is considered as related. Note that if the seriousness of an adverse event is unknown, every attempt should be made to resolve this prior to a snapshot for an interim analysis or database lock; in the exceptional case that the seriousness of an adverse event is still missing then no imputation should be applied for this characteristic.

Adverse events will be presented as “number of participants (percentage of participants) [number of events]”. In this style of output, “[number of events]” will include all cases of an AE including repeat occurrences in individual participants, while “number of participants” will count each participant only once.

Subject time at risk represents the time a participant is at risk for having an AE. The definitions for subject time at risk (in days) are outlined in Section 10.1. These definitions will be used for exposure-adjusted AE summaries.

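### SAP 10.1.2.1 runs Maintenance Period medication duration to the date of death whatever the last dose, so off-drug days can be reported as bimekizumab exposure

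*SAP*

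**What the plan says.** **Medication duration.** In both treatment periods the basic definition is last dose minus first dose in the period, plus a (redacted) dosing interval. The periods differ when a participant dies.

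- Initial Period (SAP 10.1.1.1): the rule opens "For participants who die during the Initial Period, if date of last dose in the Initial Period" plus the interval and continues "extends to a date beyond the date of death, then this calculation reverts to" date of death minus first dose plus 1. Death replaces the basic definition only when the interval after the last dose would otherwise run past it.
- Maintenance Period (SAP 10.1.2.1): "For participants who die during the Maintenance Treatment Period, then this calculation reverts to" the formula "Date of death – Date of first dose in the Maintenance Treatment Period + 1". There is no condition on the last dose.

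Section 10.1.3.1 defines the combined duration as the sum of the two periods. Section 10.1 then sorts cumulative duration into categories from more than 0 weeks up to at least 48 weeks.

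**Time at risk.** This has its own definitions. In Section 10.1.2.2 the rule for "For participants who die prior to the final visit of the Maintenance Treatment Period" is "Date of death – Date of first dose in the Maintenance Period + 1". Section 10.1.3.2 does the same for the combined period. Participants who neither die nor roll over to the extension get the smaller of last dose − first dose + 141 and last contact − first dose + 1. Section 10.2.1 ends the treatment-emergent window "through the final dose of study treatment + 140 days".

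**The concern.** Study medication duration should depend on when drug was given, not on whether the participant survived. Under 10.1.2.1, two participants with identical Maintenance dosing get different durations if one of them later dies in the period: the survivor is credited to one interval after the last dose, the other to the date of death. The Maintenance sentence has a then without an if, which suggests that a condition was lost. The SAP gives no reason for treating the periods differently.

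The number of deaths should be small, but each is examined individually, and a fatal case shown with weeks or months of exposure not received is a visible error. For time at risk, days beyond the treatment-emergent window add to a rate denominator although no countable event can occur in them, which lowers the rate.

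**Working it through.** The SAP states no exposure total to reproduce. Its window figure checks: 20 weeks × 7 = 140 days.

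**Inputs.** Initial Period 16 × 7 = 112 days (SAP 10.1.1.2). Maintenance Period 32 × 7 = 224 days (SAP 2.3.3). First Maintenance dose at Week 16. The dosing interval is redacted; 14 and 28 days are assumed. Fourteen days fits SAP Section 7: two injections per visit at 24 two-weekly visits from Week 0 to Week 46 make the stated 48.

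**Duration formulas.**
- As written: D1 = death − first Maintenance dose + 1.
- Initial Period form: D2 = last dose − first Maintenance dose + interval, replaced by D1 only if last dose + interval is after death.

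**Duration results.**

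| Last dose | Death | D1 | D2 (14 to 28 days) | Excess |
|---|---|---|---|---|
| Week 20 | Week 32 | 16×7+1 = 113 | 4×7+14 = 42 to 4×7+28 = 56 | 57 to 71 |
| Week 16 | Week 40 | 24×7+1 = 169 | 14 to 28 | 141 to 155 |
| Week 16 | just before Week 48 | 224 | 14 to 28 | 196 to 210 |

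The last row is the arithmetic maximum. If death falls within one interval of the last dose, D1 and D2 agree and the excess is 0.

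**Carry-over to the combined duration.** In the first row, adding 112 Initial days gives 112 + 113 = 225 days (32.1 weeks, so at least 32 weeks). The Initial Period form gives 112 + 42 = 154 days (22.0 weeks, at least 20) to 112 + 56 = 168 days (24.0 weeks, at least 24).

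**Time at risk.** The written rule is death − first dose + 1. With the limit it is the smaller of that and last dose − first dose + 141.
- On the planned pathway the Safety Follow-up visit is 20 weeks after the last dose (SAP 2.3.2.3) with a window of ±7 days (SAP 3.1). A death before it is at most 140 + 7 = 147 days after the last dose, so the overshoot is at most 7 days.
- With longer off-drug follow-up, a last dose at Week 16 and death at Week 40 gives 169 against 141, an excess of 28 days. The maximum (death just before Week 48) is 224 − 141 = 83 days. Within the Maintenance Period, an excess needs a last dose before about Week 28.
- For scale, 140 participants over 48 weeks contribute 140 × 336 / 365.25 ≈ 128.8 subject-years. One death adding 7 days adds 0.019 subject-years (0.015%); 28 days adds 0.077 (0.06%).

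**The case against.** The strongest reply is that the situation hardly arises. The SAP mentions participants who "prematurely discontinued study treatment but agreed to remain on the study" (Section 4.2.1.4), but that text defines the treatment policy strategy, which Table 4–1 assigns to the primary endpoint only and Section 8.2.3.4 applies to Week 16 data. A participant who stopped before Week 16 has no Maintenance dose. Section 2.3.2.3 and the notes to Figure 2-1 send those withdrawn from treatment to a 20-week Safety Follow-up, which Section 10.1.2.1 keeps apart from the Maintenance Period. A death there may not trigger the rule at all. This stands as to frequency. It does not make the rule right: missed doses, or stopping drug without yet having left the period, are enough to reach it.

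It can also be said that the death bullet sits under the preceding note and inherits its condition. That does not rescue it, because the note tests whether last dose plus interval passes the final visit date, not the date of death. If the last dose and last visit are both at Week 20 and death is at Week 32, the note's condition is met and the duration is still 113 days.

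A reader might go further and infer three things that the SAP does not support:

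- That exposure-adjusted rates are inflated or deflated by the duration rule. Medication duration does not enter the EAIR or EAER denominators, which use time at risk (Section 10.2.1).
- That the time-at-risk gap follows from the duration rule, or separates the two periods. Time at risk has its own rule, and the Initial Period version in 10.1.1.2 also runs to death without a limit. It does no harm there because 112 days is less than 140.
- That time at risk commonly exceeds the window by weeks. The planned follow-up holds the excess to about 7 days, and the SAP does not establish longer off-drug follow-up between Weeks 16 and 48.

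**Conclusion.** The Maintenance death rule in 10.1.2.1 is wrong as written. For a death in that period more than one dosing interval after the last dose, it counts off-drug days as bimekizumab exposure, contrary to the Initial Period rule for the same quantity. The excess is 57 to 71 days in the Week 20 / Week 32 example and cannot exceed 196 to 210 days for one participant. It passes into the combined duration and the cumulative categories. These figures assume an interval of 14 to 28 days and a participant still in the Maintenance Period when death occurs.

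The missing 141-day limit on time at risk for deaths is a separate and smaller inconsistency, normally worth about 7 days at most per death. Few participants are affected by either gap, the SAP gives no expected number of deaths, and the effect on pooled EAIR and EAER is negligible. This is a low-severity correction of a derivation rule. It does not touch the efficacy analyses.

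**What to change.** In 10.1.2.1, restore the condition used in 10.1.1.1: for participants who die during the Maintenance Treatment Period, revert to date of death − first Maintenance dose + 1 only if the last dose (or last bimekizumab dose, for the arm to which 10.1.1.1 applies that wording) plus the dosing interval extends beyond the date of death. Section 10.1.3.1 then needs no change, since it sums the two periods.

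In 10.1.2.2 and 10.1.3.2, for participants who die, use the minimum of date of death − first dose + 1 and last dose − first dose + 141.

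The cost is a wording change in three subsections and a small program change. Both pieces of wording already exist in the SAP.

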10.1.2.2 Time at risk (days)

Definitions for time at risk (days) are provided as follows:

- For participants who complete the Maintenance Treatment Period as planned and continue into an extension study (and, therefore, do not have the SFU visit in the feeder study):
 - Date of last visit of the Maintenance Treatment Period – Date of first dose in the Maintenance Treatment Period + 1.
- For participants who die prior to the final visit of the Maintenance Treatment Period:
 - Date of death – Date of first dose in the Maintenance Period + 1.
- For all other participants, use the minimum of the following:
 - Date of last dose in the Maintenance Treatment Period – Date of first dose in the Maintenance Treatment Period + 141 days.

- Date of last clinical contact – Date of first dose in the Maintenance Treatment Period + 1.

Note: This group could include participants who discontinue the Maintenance Treatment Period early, participants who complete the Maintenance Treatment Period as scheduled but choose not to continue into an extension study, or participants who are ongoing in the SFU period at the time of the data snapshot.

10.1.3 Exposure during the Initial and Maintenance Treatment Period

Definitions for study medication duration (days) and time at risk (days) during the Initial and the Maintenance Treatment Period are provided as follows:

10.1.3.1 Study medication duration (days)

Definitions for study medication duration (days) are provided as follows:

- Sum of study medication durations from the individual Initial and Maintenance Treatment Period.

Note: The algorithms for calculating these durations are specified in Section 10.1.1.1 and Section 10.1.2.1.

Note: If date of last dose in the Initial Treatment Period + [REDACTED] (or [REDACTED] in the case of [REDACTED] dosing) extends to a date beyond the date of first dose in the Maintenance Treatment Period, then this calculation reverts to:

- Sum of study medication durations from the individual Initial and Maintenance Treatment Periods - 1.

10.1.3.2 Time at risk (days)

Definitions for time at risk (days) are provided as follows:

- For participants who complete the Maintenance Treatment Period as planned and continue into an extension study (and, therefore, do not have the SFU visit in the feeder study):
 - Final visit date – Date of first dose + 1.
- For participants who die prior to the final visit:
 - Date of death – Date of first dose in the + 1.
- For all other participants, use the minimum of the following:
 - Date of last dose – Date of first dose + 141 days.
 - Date of last clinical contact – Date of first dose + 1.

Note: This group could include participants who discontinue early, participants who complete the Maintenance Treatment Period as scheduled but choose not to continue into an extension study, or participants who are ongoing in the SFU period at the time of the data snapshot (in the case of the interim analysis).

10.2 Adverse events

An AE is any untoward medical occurrence in a patient or clinical study participant, temporally associated with the use of IMP, whether or not considered related to the IMP. An AE can therefore be any unfavorable and unintended sign (including an abnormal laboratory finding), symptom, or disease (new or exacerbated) temporally associated with the use of IMP.

10.2.1 Data considerations

Treatment-emergent AEs are defined as those AEs that have a start date on or following the first dose of study treatment through the final dose of study treatment + 140 days (covering the 20-week SFU period). If it is not possible (due to partial dates) to determine whether or not an AE is treatment-emergent then it will be assumed to be a TEAE.

An AE will be assigned to the Initial Treatment Period if it started between the first administration of IMP on Day 1 up to Week 16. An AE will be assigned to the Maintenance Treatment Period if it started between the Week 16 study drug administration and Week 48.

If an AE occurs on the date of a treatment switch, the event is attributed to the original treatment. The only exception to this is if the AE fulfills any of the criteria specified below:

- Events that fulfill the anaphylaxis criteria for acute events (refer to Appendix A in Section 12.1)
- Hypersensitivity events identified by the SMQ “Hypersensitivity (SMQ)” (see Section 12.1 Appendix A)
- Events with an high level term (HLT) of “Administration site reactions NEC”
- Events with an HLT of “Injection site reactions”

The rules for imputing partial start or stop dates are outlined in Section 4.2.4.

Any TEAEs that occur during the SFU Period will be attributed to the period in which the participant was before initiating the SFU Period.

Duration of AEs will not be calculated if there is missing stop date information.

If the intensity of an AE is unknown, it is considered as severe. If the relationship to study drug is missing, it is considered as related. Note that if the seriousness of an adverse event is unknown, every attempt should be made to resolve this prior to a snapshot for an interim analysis or database lock; in the exceptional case that the seriousness of an adverse event is still missing then no imputation should be applied for this characteristic.

Adverse events will be presented as “number of participants (percentage of participants) [number of events]”. In this style of output, “[number of events]” will include all cases of an AE including repeat occurrences in individual participants, while “number of participants” will count each participant only once.

Subject time at risk represents the time a participant is at risk for having an AE. The definitions for subject time at risk (in days) are outlined in Section 10.1. These definitions will be used for exposure-adjusted AE summaries.

Selected AE summaries will include the exposure-adjusted incident rate (EAIR) with associated 95% CI and the exposure adjusted event rate (EAER).

The EAIR is defined as the number of participants (n) with a specific AE adjusted for the exposure and will be scaled to 100 subject-years:

$$EAIR = 100 \times n / \sum_{i=1}^N (T_{Exp(i)})$$

Where $T_{Exp(i)}$ is the exposure time and N is the number of participants at risk.

If a participant has multiple events, the time of exposure is calculated to the first occurrence of the AE being considered. If a participant has no events, the total time at risk is used.

Exact Poisson 95% confidence intervals for incidence rates are calculated using the relationship between the Poisson and the Chi-square distribution (Ulm, 1990; Fay and Feuer, 1997):

$$LCL = \chi^2_{2n, \alpha/2} / 2$$

$$UCL = \chi^2_{2(n+1), 1-\alpha/2} / 2$$

where n is the number of participants with a specific AE for the incidence rate of interest and is the basis for the number of the degrees of freedom for the chi-square quantile for the upper tail probability χ^2 .

The EAER will be the number of AEs including repeat occurrences in individual participants divided by the total time at risk scaled to 100 patient-years and calculated using:

$$EAER = 100 \times N_{AE} / \sum_{i=1}^N (T_{Risk(i)})$$

where N_{AE} is the total number of AEs, T_{Risk} is the time at risk for each participant, and N is the total number of participants at risk.

No confidence interval will be computed for EAER.

Selected summaries, as specified in Section 10.2.2, will include the risk difference between bimekizumab and placebo. The risk difference is calculated as:

$$RD = IP_{BKZ} - IP_{PBO}$$

where IP_{BKZ} is the incidence proportion for the bimekizumab-treated group and IP_{PBO} is the incidence proportion for the placebo group. Note that incidence proportion simply refers to the percentage of participants within the specified treatment group that experienced a given adverse event.

The standard error for the risk difference is calculated as follows:

$$SE_{RD} = \sqrt{\left(IP_{BKZ} \times \left(\frac{1 - IP_{BKZ}}{n_{BKZ}} \right) \right) + \left(IP_{PBO} \times \left(\frac{1 - IP_{PBO}}{n_{PBO}} \right) \right)}$$

where n_{BKZ} is the number of participants in the bimekizumab-treated group and n_{PBO} is the number of participants in the placebo group.

The corresponding confidence interval for the risk difference is as follows:

$$CI_{RD} = RD \pm Z_{1-\alpha/2} \times (SE_{RD})$$

where $Z_{1-\alpha/2}$ is the Z statistic for the corresponding level of alpha. For the risk difference confidence intervals calculated in this SAP, 1.96 will be used (corresponding to a two-sided alpha of 0.05 and 95% confidence interval). The risk difference and corresponding CI will be displayed as percentage.

